**Table 6-5 Action required for isolated total bilirubin elevation**

Abnormality	Action required
Any elevation >ULN	Fractionate bilirubin, evaluate for cholestatic liver injury (ALP) or alternative causes of bilirubin elevation. Treat alternative causes according to local institutional guidelines
Grade 2 (>1.5 - 3.0 ULN)	Maintain treatment. Repeat Liver Function Tests (LFTs) within 48-72 hours, then monitor LFTs weekly until resolution to $\leq$ Grade 1 or to baseline
Grade 3 (>3.0 – 10 ULN)	Interrupt treatment. Repeat LFTs within 48-72 hours, then monitor LFTs weekly until resolution to $\leq$ Grade 1 or to baseline
Grade 4 (> 10 x ULN)	Discontinue study treatment

If abnormalities are confirmed, close observation and follow-up are required:

1. A detailed history, including relevant information, such as cardiac disease, history of any pre-existing liver conditions or risk factors, blood transfusions, IV drug abuse, travel, work, alcohol intake, and full clinical examination for evidence of acute or chronic liver disease, cardiac disease and infection etc. should be performed.
2. Review of concomitant medications, including nonprescription medications and herbal and dietary supplement preparations, alcohol use, recreational drug use, special diets, and chemicals exposed to within one month of the onset of the liver injury.

3. Further testing for acute hepatitis A, B, C or E infection and liver imaging (e.g. biliary tract) may be warranted.
4. [REDACTED]
5. Additional testing for other hepatotropic viral infection (Cytomegalovirus, Epstein–Barr virus or Herpes-simplex virus), autoimmune hepatitis or liver biopsy may be considered as clinically indicated or after consultation with specialist/hepatologist.

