### 5.1 Inclusion criteria

Written informed consent must be signed by the patient prior to any screening procedures. Patients eligible for this study must meet **all** of the following criteria:

1. Signed informed consent must be obtained prior to participation in the study.
2. Age  $\geq 18$  years at the date of signing the informed consent form (ICF).
3. Morphologically confirmed diagnosis of a myelodysplastic syndrome (MDS) primary or secondary based on 2016 WHO classification (Arber et al 2016) by investigator assessment with one of the following Prognostic Risk Categories, based on the International Prognostic Scoring System (IPSS-R). Note: MDS diagnosis history will be recorded in the CRF:
  - Very high ( $> 6$  points)
  - High ( $> 4.5 - \leq 6$  points)
  - Intermediate ( $> 3 - \leq 4.5$  points)
4. Not suitable at time of screening for immediate myeloablative/ chemotherapy or hematopoietic stem-cell transplantation based on investigator assessment of age, comorbidities, local guidelines, institutional practice (any or all of these).
5. Eastern Cooperative Oncology Group (ECOG) performance status of 0, 1 or 2.
6. AST and ALT  $\leq 3 \times$  upper limit of normal (ULN).
7. Total bilirubin  $\leq 2 \times$  ULN (except in the setting of isolated Gilbert syndrome).
8. Estimated Glomerular Filtration Rate (eGFR)  $\geq 30$  mL/min/1.73m^2 (estimation based on Modification of Diet in Renal Disease (MDRD) formula, by local laboratory).
9. Patient is able to communicate with the investigator and has the ability to comply with the requirements of the study procedures.

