## 6.5 Dose Modification

Dose escalation is not applicable.

For participants who do not tolerate the protocol-specified dosing schedule, dose modifications consisting in dose interruptions are either recommended or mandated in order to allow participants to continue the study treatment.

Dose modifications for HMA will be done according to local practice and US package insert. Dose modifications for MBG453 (sabatolimab) will be done according to ASCO guidelines about management of immune-related AEs including hematological AEs ([Brahmer et al 2018](#)). Additionally, the guidance indicated in [Table 6-3](#) below provides instructions for infusion reaction, immune-related adverse events not covered by ASCO guidelines and a general guideline for non-hematologic non-immune-related toxicities that are clinically significant per investigator judgement and possibly attributable to the investigational drug. This general guideline will not apply in case of non-hematologic non-immune-related toxicities that are attributable to HMA or MDS and its complications.

General guidelines are to follow local practice, US package insert, and ASCO guidelines for HMAs. Further guidance is provided below.

Deviations to mandatory dose interruptions, reductions and/or permanent discontinuations are not allowed.

- **Dose modifications for MBG453 (sabatolimab)** (See [Table 6-3](#) and refer to [Brahmer et al 2018](#))

Administration of MBG453 (sabatolimab) may be delayed due to toxicities. A scheduled dose may be delayed within a cycle by up to 14 days. If a dose cannot be administered within the planned window within the cycle then the dose should be skipped. Next scheduled dosing may resume once the adverse event has resolved to  $\leq$  Grade 1 or baseline and the cycle will be shifted accordingly. Dose reductions for MBG453 (sabatolimab) are not allowed; however, longer intervals for administration (Q8W instead of Q4W) are permitted in some clinical situations, as described in [Table 6-3](#).

Overall, for adverse events of potential immune-related etiology (irAE) that do not recover to  $\leq$  Grade 1 or baseline at a dose of immunosuppression of  $\leq$  10 mg/day prednisone or equivalent (or as indicated in [section 6.5.1](#)) within 12 weeks after initiation of immunosuppressive therapy, MBG453 (sabatolimab) must be permanently discontinued.

- **Dose modifications for HMA**

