### 6.5.1 Follow-up for toxicities

Patients whose treatment is interrupted or permanently discontinued due to an AE or clinically significant laboratory value, must be followed-up at least once a week (or more frequently if required by institutional practices, or if clinically indicated) for 4 weeks, and subsequently at approximately 4-week intervals, until resolution or stabilization of the event, whichever comes first. Appropriate clinical experts should be consulted as deemed necessary.

In addition to the instructions provided in this section, please refer to Section 16.2 (Appendix 2) for further guidance on liver events, laboratory trigger definitions and follow-up requirements. For guidance on renal alert criteria, actions and events follow up, please refer to Section 16.3 (Appendix 3).

All patients must be followed up for AEs for 30 days following the last dose of azacitidine or decitabine or INQOVI (oral decitabine), or 150 days following the last dose of MBG453 (sabatolimab), whichever is later.

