**Table 6-4 Follow-up of abnormal liver chemistry results**

ALT	TBL	Liver Symptoms	Action
ALT increase without bilirubin increase:			
If normal at baseline: ALT $>3$ x	Normal		- No change to study treatment - Measure ALT, AST, ALP, GGT, TBL, INR, albumin and CK in 48- 72 hours (GLDH is recommended as well) - Follow-up for symptoms
If elevated at baseline: ALT $>2$ x baseline or $>200$ U/L (whichever occurs first)	For participants with Gilbert's syndrome: No change in baseline TBL	None	
If normal at baseline: ALT $>5$ x ULN for more than two weeks	Normal For participants with	None	- Interrupt investigational drug

If elevated at baseline: ALT >3 x baseline or >300 U/L (whichever occurs first) for more than two weeks	Gilbert's syndrome: No change in baseline TBL		
 
- Measure ALT, AST, ALP, GGT, TBL, INR, albumin and CK in 48- 72 hours (GLDH is recommended as well).
 
- Follow-up for symptoms.
 
- Initiate close monitoring and workup for competing etiologies.
 
- Investigational drug can be restarted only if another etiology is identified and liver enzymes return to baseline.
 

If normal at baseline: ALT >8 x	Normal	None	
ALT increase with bilirubin increase:			
If normal at baseline: ALT >3 x	TBL >2 x ULN (or INR >1.5)  For participants with Gilbert's syndrome: Doubling of direct bilirubin	None	
If elevated at baseline: ALT >2 x baseline or >200 U/L (whichever occurs first)			
If normal at baseline: ALT >3 x ULN	Normal or elevated	Severe fatigue, nausea, vomiting, right upper quadrant pain	
If elevated at baseline: ALT >2 x baseline or >200 U/L (whichever occurs first)			

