**Table 16-2 Follow up requirements for liver laboratory triggers with liver symptoms**

Criteria	Actions required	Follow-up monitoring
Potential Hy's Law case a	Discontinue the study treatment immediately Hospitalize, if clinically appropriate Establish causality Record the AE and contributing factors (e.g. conmeds, med hx, lab) in the appropriate CRF	ALT, AST, TBL, Alb, PT/INR, ALP and GGT until resolution c (frequency at investigator discretion)

Criteria	Actions required	Follow-up monitoring
ALT or AST		
>8 × ULN	
Discontinue the study treatment immediately
 
Hospitalize if clinically appropriate
 
Establish causality
 
Record the AE and contributing factors (e.g. comeds, med hx, lab) in the appropriate CRF
	ALT, AST, TBL, Alb, PT/INR, ALP and GGT until resolution c (frequency at investigator discretion)
>3 × ULN and INR >1.5	
Discontinue the study treatment immediately
 
Hospitalize, if clinically appropriate
 
Establish causality
 
Record the AE and contributing factors (e.g. comeds, med hx, lab) in the appropriate CRF
	ALT, AST, TBL, Alb, PT/INR, ALP and GGT until resolution c (frequency at investigator discretion)
>5 to ≤8 × ULN	
Repeat LFT within 48 hours
 
If elevation persists, continue follow-up monitoring
 
If elevation persists for more than 2 weeks, discontinue the study drug
 
Establish causality
 
Record the AE and contributing factors (e.g. comeds, med hx, lab) in the appropriate CRF
	ALT, AST, TBL, Alb, PT/INR, ALP and GGT until resolution c (frequency at investigator discretion)
>3 × ULN accompanied by symptoms b	
Discontinue the study treatment immediately
 
Hospitalize if clinically appropriate
 
Establish causality
 
Record the AE and contributing factors (e.g. comeds, med hx, lab) in the appropriate CRF
	ALT, AST, TBL, Alb, PT/INR, ALP and GGT until resolution c (frequency at investigator discretion)

>3 to $\leq$ 5 $\times$ ULN (patient is asymptomatic)	Repeat LFT within the next week  If elevation is confirmed, initiate close observation of the patient	Investigator discretion  Monitor LFT within 1 to 4 weeks
---	---	--

Criteria	Actions required	Follow-up monitoring
ALP (isolated)		

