>2 $\times$ ULN (in the absence of known bone pathology)	Repeat LFT within 48 hours  If elevation persists, establish causality  Record the AE and contributing factors (e.g. conmeds, med hx, lab) in the appropriate CRF	Investigator discretion  Monitor LFT within 1 to 4 weeks or at next visit
TBL (isolated)		
>2 $\times$ ULN (in the absence of known Gilbert syndrome)	Repeat LFT within 48 hours  If elevation persists, discontinue the study drug immediately  Hospitalize if clinically appropriate  Establish causality  Record the AE and contributing factors (e.g. conmeds, med hx, lab) in the appropriate CRF	ALT, AST, TBL, Alb, PT/INR, ALP and GGT until resolution c (frequency at investigator discretion)  Test for hemolysis (e.g. reticulocytes, haptoglobin, unconjugated [indirect] bilirubin)
>1.5 to $\leq$ 2 $\times$ ULN (patient is asymptomatic)	Repeat LFT within the next week  If elevation is confirmed, initiate close observation of the patient	Investigator discretion  Monitor LFT within 1 to 4 weeks or at next visit
Jaundice	Discontinue the study treatment immediately  Hospitalize the patient  Establish causality  Record the AE and contributing factors (e.g. conmeds, med hx, lab) in the appropriate CRF	ALT, AST, TBL, Alb, PT/INR, ALP and GGT until resolution c (frequency at investigator discretion)
Any AE potentially indicative of a liver toxicity*	Consider study treatment interruption or discontinuation	Investigator discretion

	Hospitalization if clinically	
--	-------------------------------	--

Criteria	Actions required	Follow-up monitoring
a Elevated ALT/AST >3 × ULN and TBL >2 × ULN but without notable increase in ALP to >2 × ULN		
b (General) malaise, fatigue, abdominal pain, nausea, or vomiting, or rash with eosinophilia		c Resolution is defined as an outcome of one of the following: (1) return to baseline values, (2) stable values at three subsequent monitoring visits at least 2 weeks apart, (3) remain at elevated level after a maximum of 6 months, (4) liver transplantation, and (5) death.

Based on investigator's discretion investigation(s) for contributing factors for the liver event can include: Serology tests, imaging and pathology assessments, hepatologist's consultancy; obtaining more detailed history of symptoms and prior or concurrent diseases, history of concomitant drug use, exclusion of underlying liver disease.

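### For isolated bilirubin persisting at >2 to 3.0 × ULN without known Gilbert syndrome, Table 6-5 keeps treatment going, Table 16-2 stops the study drug, and no text says which governs

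*Protocol*

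**What the plan says.** Protocol section 6.5.1.1 sends sites to Tables 6-4 and 6-5 for possible drug-induced liver injury. Table 6-5 deals with isolated total bilirubin (TBL). Its Grade 2 row (>1.5 to 3.0 × ULN) reads "Maintain treatment. Repeat Liver Function Tests (LFTs) within 48-72 hours, then monitor LFTs weekly until resolution to" Grade 1 or lower, or baseline. It makes no exception for Gilbert syndrome and sets no symptom condition. Grade 3 (>3.0 to 10 × ULN) calls for interruption, and Grade 4 (>10 × ULN) for discontinuation.

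Section 6.5.1 then adds the appendix: "In addition to the instructions provided in this section, please refer to Section 16.2 (Appendix 2) for further guidance on liver events". In that appendix, the isolated-TBL part of Table 16-2 has a row for values above 2 × ULN "in the absence of known Gilbert syndrome". It asks for repeat liver tests within 48 hours, and then: "If elevation persists, discontinue the study drug immediately".

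Two other places bear on the same patient. Table 6-3 tells sites to delay MBG453 for a Grade 2 non-hematologic, non-immune toxicity that is clinically significant and at least possibly due to MBG453. Section 6.5 states: "Deviations to mandatory dose interruptions, reductions and/or permanent discontinuations are not allowed".

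**The concern.** A rule on stopping treatment for liver toxicity should give one instruction for one set of laboratory values. Here a participant whose isolated bilirubin stays a little above twice the upper limit is to be kept on treatment under one table and taken off under another, and section 6.5.1 tells the site to use both.

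Inclusion criterion 7 makes the band easy to reach. It admits participants with TBL up to 2 × "ULN (except in the setting of isolated Gilbert syndrome"), and 2 × ULN is the lower edge of the overlap.

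What is at stake is how patients are handled. A second, smaller matter is how the planned summaries of discontinuations and interruptions are read: the action taken for such a participant could depend on which table the site opened.

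**Working it through.** The plan gives no figure to reproduce. The check intersects the bilirubin bands, compares the actions, and looks for a rule of precedence.

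**1. Overlap.** Table 6-5 Grade 2 covers (1.5, 3.0] × ULN. The Table 16-2 row covers everything above 2 × ULN, with no upper limit. The intersection is (2, 3.0] × ULN.

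**2. Actions by band** (isolated TBL, persisting on repeat, no known Gilbert syndrome):

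| TBL, × ULN | Table 6-5 | Table 16-2 | Compatible? |
|---|---|---|---|
| >1.5 to 2 | continue, monitor | repeat test, close observation (asymptomatic) | yes |
| >2 to 3.0 | continue, weekly tests | stop at once | **no** |
| >3.0 to 10 | interrupt | stop at once | both can be done |
| >10 | stop | stop at once | yes |

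**3. Does the Table 6-5 row cover a persisting elevation?** Yes. It asks for weekly tests until the value comes down. An elevation that clears on the repeat test raises no conflict.

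**4. Is Table 16-2 confined to symptomatic patients?** Its title mentions liver symptoms, but this row sets no symptom condition, while other rows of the table say explicitly whether symptoms are present or absent. Table 16-1 also classes TBL above 2 × ULN without Gilbert syndrome as a liver event, again with no symptom condition. Even if the row were limited to symptomatic patients, Table 6-5 has no such limit, so those patients would still face both orders.

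**5. Could the stop be a temporary hold?** The glossary defines study drug discontinuation as permanent. Even a hold would contradict an instruction to keep treatment going.

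**6. Third instruction.** If the investigator judges the event clinically significant and possibly due to MBG453, Table 6-3 delays MBG453 until Grade 1 or baseline. That is neither continuing nor stopping permanently.

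**7. Precedence.** The bar on deviations in section 6.5 protects mandatory interruptions and discontinuations but does not say which table is the mandatory one. Neither the protocol nor the SAP ranks the tables.

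**8. Distance from entry to the band.** The relative rise needed from baseline b (in × ULN) to reach the lower edge is 2.0/b − 1. At b = 1.0 it is 2.0/1.0 − 1 = 100%. At the entry limit, b = 2.0, it is zero, so any rise enters the band. These baselines are illustrative. The documents give no baseline distribution, so this shows where the band lies and not how many participants reach it.

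**The case against.** The strongest reply is that sites are not left helpless. The protocol describes Tables 6-4 and 6-5 as guidelines and Appendix 2 as further guidance. The bar on deviations points towards the stricter action. Section 9.1.1 requires the investigator to stop treatment when continuing would harm the participant, and for laboratory abnormalities that in the investigator's judgement prevent continued participation. All of this is correct, and it lowers the risk to patients. It does not settle the text: both sets of tables carry a guidance label, and discretion to stop does not say whether the row that says to continue still applies.

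A second reply is that nothing analytic follows. The trial is descriptive, with no hypothesis test, and the SAP document history dates its last update after database lock. This stands. A reader might infer that the adverse event or laboratory results are biased, but the documents do not support that. SAP section 2.8.3 grades laboratory results from observed values alone, whichever rule a site followed. A reader might also turn one participant in 39 into a shift of 2.6 percentage points (1/39) in a discontinuation rate. That is only the size of the denominator; nothing shows that even one participant entered the band.

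A third reply is that the neighbouring mismatches are weaker, and this also stands:

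- **TBL >3.0 to 10 × ULN.** A site can interrupt and then discontinue without breaching either table.
- **ALT >5 to 8 × ULN for more than two weeks.** Table 16-2 says "If elevation persists for more than 2 weeks, discontinue the study drug", while Table 6-4 interrupts and adds "Investigational drug can be restarted only if another etiology is identified and liver enzymes return to baseline". These clash only if the stop is permanent. The rows of Table 6-4 are also broken in the text available for review, so matching row to action is less certain there.
- **Drug to be stopped.** It is tempting to say a site cannot tell which drug Table 16-2 means. Section 6.1 applies the term study drugs to both components, and Table 6-2, which carries that title, lists only the HMAs. But the Table 6-3 title and the glossary entry for investigational drug both favour MBG453. This is a wording repair and not a separate fault.

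**Conclusion.** The inconsistency is real and narrow. It concerns isolated TBL persisting on repeat at >2 to 3.0 × ULN in a participant without known Gilbert syndrome. There, Tables 6-5 and 16-2 give incompatible dosing instructions, Table 6-3 can add a third, and no text says which governs.

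The conclusion rests on reading the two isolated-TBL rows as written and on section 6.5.1 making them additive. It does not depend on the meaning of study drug, because stopping either component is incompatible with keeping treatment going.

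Its size in participants is unknown: the documents give no frequency for these elevations, and the count could be zero. It deserves correction because it is a safety rule that is wrong as written and cheap to mend.

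**What to change.** **If the protocol text is reused**

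- Split the Table 6-5 Grade 2 row at 2 × ULN, so that isolated TBL persisting above 2 × ULN without known Gilbert syndrome follows the Table 16-2 action. Alternatively, state in section 6.5.1 that the strictest applicable action among Tables 6-3, 6-5 and 16-2 governs.
- Name the drug to be stopped in that row: MBG453, HMA or both.
- In the same edit, align the ALT >5 to 8 × ULN rows of Tables 6-4 and 16-2, either as a permanent stop or as an interruption with conditional restart.

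**For this trial**

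- Add one listing to the clinical study report of any participant with recorded isolated TBL above 2 × ULN and no known Gilbert syndrome, showing any repeat values and the recorded dosing action for each drug.
- Do not require proof of persistence. Table 8-1 schedules chemistry on Day 1 of cycles 1 to 7 and then at cycles 9, 11 and 13 of the core phase, so a 48-hour repeat appears only if an unscheduled result was entered.
- Do not try to attribute which table a site followed. The dose-change reasons that SAP section 2.4.1 gives as examples, for HMA, do not record it.

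**Cost.** A text edit, and one listing covering at most 39 participants. SAP section 2.8.3 already lists all laboratory data by subject and visit, and the protocol requires dose changes to be recorded. The stricter rule might bring a few more discontinuations in a future trial.

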#### **6.5.1.2 Follow-up for QTcF Prolongation**

In case of QTcF >480 ms (or QTcF prolongation >60 ms from baseline):

- Assess the quality of the ECG recording. Collect two additional ECGs as soon as possible.
- Determine the serum electrolyte levels (in particular hypokalemia, hypomagnesemia). If abnormal, correct abnormalities.
- Review concomitant medication use for possible causes for QT prolongation (refer to [crediblemedicines.org](http://crediblemedicines.org)). Record all concomitant medications in the appropriate eCRF page.
- Monitor ECG per the institutional standards.
- Contact Novartis Medical Lead in case QTcF >500 ms or QTcF prolongation >60 ms from baseline.

### **6.6 Additional treatment guidance**

#### **6.6.1 Treatment compliance**

The date and time of all study treatment administrations during the study and any deviations from the protocol treatment schedule will be captured by the investigator staff on the appropriate study treatment dispensing form. This information must be captured in the source document at each patient visit. Compliance with the study treatment and any protocol deviations will be assessed by the field monitor on an ongoing basis. All study treatment dispensed and returned (if applicable) must be recorded in the Drug Accountability Log.

MBG453 (sabatolimab) will be administered to the patient by the study site staff. Decitabine or azacitidine (IV/SC) will be administered per site regulations. This may include administration by study site staff, or local administration at another hospital or through home administration by qualified site staff, or by trained non-study personnel. Compliance will be assured by administration of the study treatment under the supervision of investigator or his/her designee.

All dosages for MBG453 (sabatolimab) well as HMAs prescribed to the participant and all dose changes during the study must be recorded on the corresponding Dosage Administration Record eCRF.

